**Figure 3. Graphical Multiple Testing Procedure for US/FDA Regulatory Purposes**

**Figure 4. Graphical Multiple Testing Procedure for EU/EMA Regulatory Purposes**

### 9.2.6 Efficacy Subgroup Analysis

The primary efficacy endpoint will be examined in the subgroups listed in [Table 3](#) below. Treatment difference between each Upadacitinib dose and the combined placebo group will be presented with point estimate and 95% confidence interval using normal approximation. No p-value will be provided for subgroup analysis. If any of the resulting subgroups has fewer than 10% of the planned study size (i.e., < 45 subjects), the subgroup analyses for that variable will not be presented.

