###### **8.1.4.1.1 Primary Efficacy Variable**

The primary endpoint (at Week 12) for US/FDA regulatory purposes is listed in Section 5.3.3.1.1. The primary endpoint (at Week 12) for EU/EMA regulatory purposes is also listed in Section 5.3.3.1.1. Analyses will be conducted separately for US/FDA regulatory purposes and EU/EMA regulatory purposes; for each set of analysis, only one primary endpoint is specified.

Analysis of the primary endpoint will be conducted on the FAS based on treatment as randomized. Comparisons of the primary endpoint will be made between each upadacitinib dose and the combined placebo group using the Cochran-Mantel-Haenszel test adjusting for main stratification factors. For the primary analysis, non-responder

imputation (NRI) will be used. The analysis will be repeated using Observed Cases (OC). Supportive analysis will also be conducted on the Per Protocol Analysis Set.

The primary efficacy analyses will be performed in demographic subgroups including age, gender, weight, body mass index, race, and geographical region to assess the consistency of the treatment effect. Additional subgroup analyses based on baseline disease characteristics and stratification factors will also be conducted.

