## **4.3 Sample Size**

The planned total sample size of 450 can provide approximately 90% power to detect a 20% difference in ACR20 rates at Week 12 (assuming a placebo ACR20 response rate of 27%), at two-sided  $\alpha = 0.025$  and accounting for 10% dropout rate. This sample size also provides approximately 90% power for a 17% difference in DAS28 (CRP) LDA response rate at Week 12 (assuming a placebo DAS28 LDA response rate of 12%), at two-sided  $\alpha = 0.025$  and accounting for 10% dropout rate. It can also provide at least 90% power

for most key secondary endpoints, at two-sided significance level of 0.025 and accounting for a 10% dropout rate.

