**Table 3. Subgroups for Efficacy Analysis**

Subgroup Factor	Categories
Age	< 40, [40, 65), ≥ 65
Sex	Male or Female
Weight	< 60 kg or ≥ 60 kg
BMI	< 25 or ≥ 25
Race	White, Black or African American, American Indian or Alaska Native, Native Hawaiian or Other Pacific Islander, Asian, Other
Geographic Region	North America, South/Central America, Western Europe, Eastern Europe, Asia, Other
Duration of RA diagnosis	< 10 year or ≥ 10 year
Baseline Rheumatoid Factor Status	Positive or Negative
Baseline Anti-CCP Antibody Status	Positive or Negative
Baseline both RF positive and Anti-CCP positive	Yes or No
Baseline DAS28[hsCRP)	≤ 5.1 or > 5.1
Prior failed bDMARD	stratum 1: failed 1 or 2 biologics with the same mechanism of action; stratum 2: failed ≥ 3 biologics with the same mechanism of action and/or multiple mechanisms of action
Failed at least one Prior bDMARD due to lack of efficacy	Yes or No
Failed anti-IL6 due to lack of efficacy	Yes or No

### 9.2.7 Summary of Efficacy Analysis by Week 12

Table 4 below provides the overview of the efficacy analyses by Week 12 to be performed on different endpoints.

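### The SAP's 45-subject rule withholds a whole subgroup variable when one category is small, so race, region or age can go unreported although the protocol commits to them without a size condition

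*SAP*

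**What the plan says.** Protocol section 8.1.4.1.1 says: "The primary efficacy analyses will be performed in demographic subgroups including age, gender, weight, body mass index, race, and geographical region". It gives the purpose as checking that the treatment effect is consistent, and sets no minimum size. It adds: "Additional subgroup analyses based on baseline disease characteristics and stratification factors will also be conducted". Geographic region is one of the two stratification factors, so the protocol commits to it twice.

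SAP section 9.2.6 says the primary endpoint will be examined in the Table 3 subgroups, with point estimates, 95% normal-approximation intervals and no p-values. It then limits what is shown. The trigger is worded "If any of the resulting subgroups has fewer than 10% of the planned study size"; the SAP works this limit out as 45. The stated consequence is that "the subgroup analyses for that variable will not be presented".

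SAP Table 3 lists 14 factors. Eleven have two levels. The other three are:
- race, in six levels: "White, Black or African American, American Indian or Alaska Native, Native Hawaiian or Other Pacific Islander, Asian, Other";
- age, in three levels: under 40, 40 to under 65, and 65 or over;
- region, again in six levels: "North America, South/Central America, Western Europe, Eastern Europe, Asia, Other".

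Neither document says how to combine small categories or how to suppress one category alone. Neither gives an expected or observed count by race, region or age.

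**The concern.** The rule is triggered by a category but acts on the variable. A minimum size is meant to keep unstable estimates out of the report. This one also removes the stable estimates, because a small category sits beside them in the table.

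Take an illustrative enrolment of 300 White and 100 Asian subjects, with the remaining 50 split 30 and 20 over two other race levels. Two levels fall under 45, so nothing is shown for race, although two levels hold 400 of the 450 subjects.

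What is at stake is the consistency assessment that the protocol promises for race, region and age. The primary test, the type I error control and the ranked endpoints are not affected.

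**Working it through.** **Inputs.** The planned size is 450 (SAP section 4.3: "The planned total sample size of 450 can provide approximately 90% power to detect a 20% difference in ACR20 rates"). The threshold, number of levels and unit of suppression come from SAP section 9.2.6 and Table 3. Category shares are assumptions, because the documents give none, so a range is shown.

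**Step 1: the plan's own figure.** 10% × 450 = 45. The SAP's threshold is reproduced.

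**Step 2: what a six-level variable needs.** If all six levels are occupied, each must hold at least 45, and 6 × 45 = 270 of 450 (60%). The largest level can then hold at most 450 − 5 × 45 = 225 (50%). An equal split gives 450 / 6 = 75 per level, so display is arithmetically possible. If all six levels are occupied and one holds more than half of the subjects, the variable is certain to be withheld.

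**Step 3: chance that one level reaches 45.** For a level with true share s, the count X is binomial(450, s), and P(X ≥ 45) is:

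| Share s | P(X ≥ 45) |
|---|---|
| 2% | 3 × 10⁻¹⁸ |
| 5% | 0.00001 |
| 8% | 0.07 |
| 10% | 0.52 |
| 12% | 0.92 |
| 15% | 0.999 |

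**Step 4: chance that all six levels reach 45.** These are multinomial probabilities with N = 450, and the remaining levels share the rest equally:

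| Assumed mix | P(variable is shown) |
|---|---|
| all six equal | 99.99% |
| smallest level 12% | 92% |
| smallest level 10% | 52% |
| two levels at 10% | 26% |
| smallest level 8% | 7% |
| two levels at 8% | 0.4% |
| two smallest levels at 8% and 6% | about 0.0025% |
| smallest level 5% | about 0.001% |

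**Step 5: age.** If the other two age groups are comfortably above 45, the variable is lost with probability 1 − P(X ≥ 45) for the under-40 group. That is 1 − 0.523 = 48% at a 10% share and 1 − 0.073 = 93% at 8%.

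**Step 6: empty levels.** The rule refers to resulting subgroups, so a listed level with no subjects may not count. The chance that a level is empty is (1 − s)^450. At s = 0.5% this is 0.995^450 = 0.10; at s = 1% it is 0.01. On that reading a level with no subjects leaves the variable in the report and a level with one subject removes it.

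**The case against.** Five points can be made for the plan.

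1. **A size limit is sensible.** With the placebo groups combined, allocation is 1:1:1, so 45 subjects is about 15 per analysis arm. At the planning rates of 27% and 47%, the 95% half-width for the difference in ACR20 is 1.96 × √(0.27 × 0.73/15 + 0.47 × 0.53/15) = 0.34. This stands, but it supports withholding the small category, not the large ones beside it.

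2. **The protocol leaves detail to the SAP.** Protocol section 8.1 says so, and the SAP still says the endpoint will be examined in every Table 3 subgroup; only presentation is limited. This softens the conflict without removing it. A consistency assessment that is run but not shown does not serve the protocol's stated purpose.

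3. **Nothing inferential depends on it.** These analyses carry no p-value. That is correct and limits the weight of the point. It also means that changing the rule costs nothing in type I error.

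4. **The analysis is done.** SAP section 11.1 says the primary analysis and Period 1 reporting were completed under version 2.0, and that version 3.0 governs only future long-term reporting. SAP Table 11 says version 2.0 incorporated FDA feedback. The text of version 2.0 is not available here, so whether it held the same rule is unknown. This stands: rewording version 3.0 does not change the completed analysis, and pooling chosen now is post hoc.

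5. **The argument does not reach every factor.** For the eleven two-level factors, suppressing the small level leaves no contrast and there is nothing to pool. The point is confined to race, region and age.

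**Conclusion.** The concern holds as a defect in a stated rule. One category under 45 withholds a whole multi-level variable, no pooling rule exists, and the protocol's commitment to race, region and age carries no size condition. That much needs no assumption about enrolment.

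How often the rule bites does depend on enrolment:
- **Race** is almost certainly lost if any non-empty level holds about 5% or less. Native Hawaiian or Other Pacific Islander and American Indian or Alaska Native are the obvious candidates, but that is an assumption.
- **Region** may be shown if its smallest level holds about 12% or more (92% with one level at 12%). It is very likely lost if the smallest level holds 8% or less (shown in 7% of trials at best).
- **Age** is close to a coin toss if 10% of subjects are under 40.

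A reader might infer that race can never be shown and that region very probably will not be. The documents do not support this. They give no enrolment mix, the chance of display runs from 99.99% to practically zero over the mixes above, and a level with no subjects may not count at all.

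The change should be made. Its weight is limited to descriptive reporting.

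**What to change.** In SAP section 9.2.6:
- apply the 45-subject limit to the category instead of the variable;
- pool levels under 45 by a rule stated in advance, for example into Other for race and region, and into the adjacent group for age;
- present the variable with the remaining categories;
- state that levels with no subjects are ignored.

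For the completed primary analysis, state which Table 3 variables were withheld, if any. Supply any withheld race, region or age results with the pooled categories, labelled post hoc.

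The cost is a short SAP edit, one recode and, where results were withheld, a supplementary table. No test or alpha is affected. The downside is that pooled categories are less specific, and a pooled level may itself stay under 45. In that case it is left out and the other categories are still shown.

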**Table 3. Subgroups for Efficacy Analysis**

Subgroup Factor	Categories
Age	< 40, [40, 65), ≥ 65
Sex	Male or Female
Weight	< 60 kg or ≥ 60 kg
BMI	< 25 or ≥ 25
Race	White, Black or African American, American Indian or Alaska Native, Native Hawaiian or Other Pacific Islander, Asian, Other
Geographic Region	North America, South/Central America, Western Europe, Eastern Europe, Asia, Other
Duration of RA diagnosis	< 10 year or ≥ 10 year
Baseline Rheumatoid Factor Status	Positive or Negative
Baseline Anti-CCP Antibody Status	Positive or Negative
Baseline both RF positive and Anti-CCP positive	Yes or No
Baseline DAS28[hsCRP)	≤ 5.1 or > 5.1
Prior failed bDMARD	stratum 1: failed 1 or 2 biologics with the same mechanism of action; stratum 2: failed ≥ 3 biologics with the same mechanism of action and/or multiple mechanisms of action
Failed at least one Prior bDMARD due to lack of efficacy	Yes or No
Failed anti-IL6 due to lack of efficacy	Yes or No

### 9.2.7 Summary of Efficacy Analysis by Week 12

Table 4 below provides the overview of the efficacy analyses by Week 12 to be performed on different endpoints.

**Table 4. Summary of Efficacy Variables and Corresponding Analyses for Efficacy Analysis by Week 12**

Efficacy Variables	Analysis Method
Primary Variables	

 
• ACR20 response at Week 12a
 
• LDA as measured by DAS28(CRP) at Week 12b
 
	
 
• Point estimate and 95% CI of the response rate for each Upadacitinib dose group and the combined placebo group. The 95% CI will be based on normal approximation.
 
• Point estimate, 95% CI and p-value for the treatment comparison between each Upadacitinib dose group and the combined placebo group, where the p-value is constructed using the Cochran-Mantel-Haenszel test adjusting for stratification factor prior bDMARD use. Both nominal p-value and adjusted p-value through the graphical multiplicity procedure described in Section 9.2.5 will be provided. The 95% CI will be based on normal approximation.
 
• Subgroup analysis.
 
• Imputation: NRI for primary analysis and OC for sensitivity analysis
 
• Analysis Set: FAS and Per Protocol Analysis Set as supportive analysis (NRI only).
 

Key Secondary Variables	

Binary Endpoints:
 
 
• ACR50/70 response at Week 12
 
• ACR20 response at Week 12b
 
• LDA as measured by DAS28(CRP) at Week 12a
 
• ACR20 response at Week 1
 
	
 
• Point estimate and 95% CI of the response rate for each treatment group. The 95% CI will be based on normal approximation.
 
• Point estimate, 95% CI and p-value for the treatment comparison between each Upadacitinib dose group and the combined placebo group using the Cochran-Mantel-Haenszel test adjusting for stratification factor prior bDMARD use. For ranked key secondary endpoints, both nominal p-value and adjusted p-value through the graphical multiplicity procedure described in Section 9.2.5 will be provided. The 95% CI will be based on normal approximation.
 
• Imputation: NRI for primary analysis and OC for sensitivity analysis
 
• Analysis Set: FAS
 

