## **9.2 Efficacy Analysis by Week 12**

### **9.2.1 Primary Efficacy Analysis**

The primary endpoint for US/FDA regulatory purposes is ACR20 response at Week 12. The primary endpoint for EU/EMA regulatory purposes is LDA (based on DAS28 (CRP)  $\leq 3.2$ ) at Week 12. Analyses will be conducted separately for US/FDA regulatory purposes and EU/EMA regulatory purposes; for each set of analysis, only one primary endpoint is specified.

Analysis of the primary endpoint will be conducted on the FAS based on randomized treatment groups (Upadacitinib 15 mg QD, Upadacitinib 30 mg QD and the combined placebo groups). Point estimate and 95% CI using normal approximation will be

provided for the response rate for each randomized treatment group. Comparisons of the primary endpoint will be made between each Upadacitinib dose and the combined placebo group using the Cochran-Mantel-Haenszel test adjusting for stratification factor prior bMDARD use. Point estimate, 95% CI using normal approximation and p-value for the treatment comparison will be presented. Both the nominal p-value constructed using the Cochran-Mantel-Haenszel test and the adjusted p-value through the graphical multiplicity procedure described in Section 9.2.5 will be provided. For the primary analysis, non-responder imputation (NRI) will be used.

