### **9.2.3 Key Secondary Efficacy Analyses**

Ranked key secondary endpoints (at Week 12) for US/FDA regulatory purposes are:

1. Change from baseline in DAS28 (CRP);
2. Change from baseline in HAQ-DI;
3. LDA as measured by DAS28 (CRP);
4. Change from baseline in SF-36 Physical Component Score (PCS).

Ranked key secondary endpoints (at Week 12) for EU/EMA regulatory purposes are:

1. Change from baseline in DAS28 (CRP);
2. ACR20 response rate;
3. Change from baseline in HAQ-DI;

4. Change from baseline in SF-36 Physical Component Score (PCS).

Other key secondary endpoints (at Week 12) for both US/FDA and EU/EMA regulatory purposes are:

1. ACR50 response rate;
2. ACR70 response rate;
3. ACR20 response rate at Week 1.

For binary endpoints, frequencies and percentages will be reported for each randomized treatment group. Similar analyses as for the primary endpoint will be conducted.

For the major RA continuous endpoints DAS28 and HAQ-DI change from baseline, statistical inference will be conducted using analysis of covariance (ANCOVA) coupled with MI for missing data handling. Specifically, the ANCOVA model will include treatment as the fixed factor, and the corresponding baseline value and the stratification factor prior bDMARD use (Yes/No) as the covariates. For other continuous endpoints, statistical inference will be conducted using the MMRM model as described in Section 9.1.2, with the main stratification factor being prior bDMARD use (Yes/No). From both the MI and MMRM analyses, the LS mean and 95% CI will be reported for each randomized treatment group; the LS mean treatment difference and associated 95% CI and p-value will be reported comparing each Upadacitinib dose group with the combined placebo group. Both nominal p-value and adjusted p-value through the graphical multiplicity procedure described in Section 9.2.5 will be provided.

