### 9.2.5 Handling of Multiplicity

The overall type I error rate of the primary and ranked key secondary endpoints for the two doses will be strongly controlled using a graphical multiple testing procedure. Specifically, the testing will utilize the endpoint sequence of primary endpoint followed by the ranked key secondary endpoints in the order as specified in Section 9.2.3, and will begin with testing the primary endpoint using  $\alpha$  of 0.025 for each dose. Continued testing will follow a pre-specified  $\alpha$  transfer path which includes downstream transfer along the endpoint sequence within each dose as well as cross-dose transfer. Adjusted p-values for the primary and ranked key secondary endpoints will be provided based on the testing procedure.

[figure not shown]
The graphs for the testing procedures are provided in Figure 3 and Figure 4, for US/FDA and EU/EMA regulatory purposes respectively. In the graph, the arrows specify the  $\alpha$  transfer paths. Once an endpoint is rejected (i.e., deemed significant) at its assigned significance level, its significance level will be transferred to subsequent endpoint(s) following the arrow(s). The numbers on the arrows denote the weights for transferring significance levels. Specifically, the weight 1 denotes 100% transfer of significance level.

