**Table 4. Summary of Efficacy Variables and Corresponding Analyses for Efficacy Analysis by Week 12 (Continued)**

Efficacy Variables	Analysis Method
Key Secondary Variables (Continued)	
Continuous Endpoints: 
 
• Change from baseline in DAS28(CRP) at Week 12
 
• Change from baseline in HAQ-DI at Week 12
 
	
 
• LS mean, and 95% CI within each treatment group and LS mean, 95% CI and p-values between each Upadacitinib dose group and the combined placebo group using ANCOVA model with treatment, prior bDMARD use and baseline value as covariates. Both nominal p-value and adjusted p-value through the graphical multiplicity procedure described in Section 9.2.5 will be provided.
 
• Imputation: MI
 
• Analysis Set: FAS
 

Change from baseline in SF-36 Physical Component Score (PCS) at Week 12	
 
• LS mean and 95% CI within each treatment group and LS mean, 95% CI and p-values between each Upadacitinib dose group and the combined placebo group using MMRM model with fixed effects of treatment, visit and treatment-by-visit interaction, prior bDMARD use and baseline value as covariate. Both nominal p-value and adjusted p-value through the graphical multiplicity procedure described in Section 9.2.5 will be provided.
 
• Analysis Set: FAS
 

Additional Variables (summarized at all visits up to Week 12)	
Binary Endpoints: 
 
• ACR20/50/70
 
• LDA and CR based on DAS28(CRP), DAS28 (ESR), SDAI, and CDAI criteria
 
• Proportion of subjects achieving MCID in change from baseline in HAQ-DI among those with baseline HAQ-DI <math>\geq 0.3</math>;
 
• ACR/EULAR Boolean remission;
 
	
 
• Point estimate and 95% CI of the response rate for each treatment group. The 95% CI will be based on normal approximation.
 
• Point estimate, 95% CI and p-value for the treatment comparison between each Upadacitinib dose group and the combined placebo group using the Cochran-Mantel-Haenszel test adjusting for stratification factor prior bDMARD use. Only nominal p-value will be provided, and the 95% CI will be based on normal approximation.
 
• Imputation: NRI for primary analysis and OC for sensitivity analysis
 
• Analysis Set: FAS
 

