**Table 7. Anatomical Joints for DAS28 (CRP) Calculation**

Shoulder	Elbow	Wrist	Thumb Interphalangeal
Metacarpophalangeal I	Metacarpophalangeal II	Metacarpophalangeal III	Metacarpophalangeal IV
Metacarpophalangeal V	Proximal Interphalangeal II	Proximal Interphalangeal III	Proximal Interphalangeal IV
Proximal Interphalangeal V	Knee		

To calculate observed DAS28 scores, the observed component value will be calculated first. Then the components will be included in the calculation per the DAS formula selected. If any observed component is missing in a window, then the observed DAS28 score will be missing.

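### Week 12 low disease activity, the EU primary endpoint, is tested without baseline DAS28(CRP): a valid test, but one that forgoes a modest gain in power

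*SAP*

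**What the plan says.** SAP 9.2.1 states: "The primary endpoint for EU/EMA regulatory purposes is LDA", defined as DAS28(CRP) at or below 3.2 at Week 12. The comparison of each dose with combined placebo is made "using the Cochran-Mantel-Haenszel test adjusting for stratification factor prior bMDARD use", with non-responder imputation (NRI) on the Full Analysis Set. Table 4 repeats this for the primary variables ("where the p-value is constructed using the Cochran-Mantel-Haenszel test adjusting for stratification factor prior bDMARD use"). It uses the same test where LDA is the third-ranked US secondary. Protocol 8.1.4.1.1 names only the main stratification factors.

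The continuous endpoints are handled differently. For change in DAS28(CRP) and HAQ-DI, SAP 9.2.3 specifies ANCOVA with "the corresponding baseline value and the stratification factor prior bDMARD use (Yes/No) as the covariates", and Table 4 confirms it ("using ANCOVA model with treatment, prior bDMARD use and baseline value as covariates"). The mixed model for SF-36 PCS also includes its baseline value.

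Baseline DAS28(CRP) otherwise appears in two places. It is a tabulated baseline characteristic (SAP 6.1), and it is a subgroup factor split at 5.1 (Table 3), reported without a p-value. Neither analysis in SAP 9.2.2 (observed cases; NRI on the Per Protocol set) brings it into the LDA comparison.

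**The concern.** LDA is a fixed cut on the DAS28(CRP) scale, so how far above 3.2 a subject starts should bear on the chance of getting below it. The entry criteria leave that distance wide. Two illustrative profiles, put into the SAP 9.4.6 formula:

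- TJC28 = SJC28 = 6, hsCRP 3 mg/L, PtGA 30 mm: 1.37 + 0.69 + 0.50 + 0.42 + 0.96 = 3.9, which needs a fall of about 0.7.
- TJC28 = 20, SJC28 = 15, hsCRP 20 mg/L, PtGA 80 mm: 2.50 + 1.08 + 1.10 + 1.12 + 0.96 = 6.8, which needs a fall of about 3.6.

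Randomisation is stratified by prior bDMARD failure and region, not by disease activity. A chance imbalance in baseline DAS28(CRP) is therefore handled neither by the design nor by the LDA test. At stake is some power on the test that opens the EU sequence, and protection of that result against imbalance.

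**Working it through.** **Inputs from the documents.** Protocol 8.2 and SAP 4.3: 450 subjects, placebo LDA 12%, difference 17 points (so 29% on active), two-sided alpha 0.025, 10% dropout, power about 90%. SAP 9.2.5: alpha "of 0.025 for each dose". Design: 150 per dose against 75 + 75 = 150 on placebo. Evaluable per arm: 150 × 0.9 = 135.

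**Step 1: the plan's own figure.** Pooled rate 0.205. Null SE = √(2 × 0.205 × 0.795 / 135) = 0.0491. Alternative SE = √((0.12 × 0.88 + 0.29 × 0.71) / 135) = 0.0480. Power = Φ((0.17 − 2.241 × 0.0491) / 0.0480) = Φ(1.246) = 0.894. Exact enumeration of the chi-square test gives 0.900. The stated 90% is reproduced without any baseline adjustment.

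**Step 2: power with baseline added.** The documents give no correlation r between baseline and Week 12 DAS28(CRP), so r is an assumption, shown over a range. With a normal latent Week 12 score and standardised baseline x, the response probability in an arm with rate p is π(x) = Φ((Φ⁻¹(p) − r x) / √(1 − r²)). The ratio of adjusted to unadjusted variance is

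f = [2 E{π₀(1 − π₀)} + 2 E{π₁(1 − π₁)} + Var(π₁ − π₀)] / [2 (0.12 × 0.88 + 0.29 × 0.71)].

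Power is Φ((1.246 + 2.241) / √f − 2.241). The evaluable number per arm that keeps the planned power is 135 f.

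**Step 3: simulation of the planned test.** 6,000 trials per setting, marginal rates 12% and 29%, 35% of subjects in prior-bDMARD stratum 2, and an assumed small stratum effect. The comparison is CMH by prior bDMARD against a logistic score test that adds continuous baseline DAS28(CRP). The NRI columns use 150 per arm with 10% set to non-response.

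| Assumed r | f | Power by formula (0.894 without baseline) | Per arm for planned power | NRI, 150 per arm: CMH / adjusted | 135 per arm: CMH / adjusted |
|---|---|---|---|---|---|
| 0 | 1.000 | 0.894 | 135 | 0.895 / 0.896 | 0.902 / 0.903 |
| 0.2 | 0.981 | 0.900 | 132 | 0.892 / 0.897 | 0.904 / 0.910 |
| 0.3 | 0.956 | 0.907 | 129 | 0.890 / 0.903 | 0.892 / 0.908 |
| 0.4 | 0.921 | 0.918 | 124 | 0.896 / 0.918 | 0.893 / 0.921 |
| 0.45 | 0.898 | 0.925 | 121 | not run | not run |
| 0.5 | 0.873 | 0.932 | 118 | 0.886 / 0.925 | 0.907 / 0.945 |
| 0.6 | 0.810 | 0.949 | 109 | 0.894 / 0.947 | 0.901 / 0.957 |

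The Monte Carlo SE of a single power figure is √(0.9 × 0.1 / 6000) = 0.004. A second simulation of the NRI setting gave 0.886 to 0.896 without baseline. With baseline it gave 0.895, 0.900, 0.924 and 0.941 at r = 0.2, 0.3, 0.45 and 0.6.

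**Step 4: the 5.1 cut as an extra CMH stratum.** With assumed baseline mean 5.8 and SD 1.0, NRI setting, CMH power moves from 0.892 to 0.890 at r = 0.2, from 0.890 to 0.897 at r = 0.3, from 0.886 to 0.909 at r = 0.5 and from 0.894 to 0.924 at r = 0.6. That recovers less than the continuous covariate, and nothing at low r.

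**Step 5: type I error.** At r = 0.5, rejection in the favourable direction is 0.0125 for CMH and 0.0138 for the adjusted score test. The nominal value is 0.0125 with a Monte Carlo SE of √(0.0125 × 0.9875 / 6000) = 0.0014. In the second simulation, two-sided null rejection was 2.2% to 2.8% against 2.5%.

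**The case against.** **No error and nothing promised is missing.** CMH is a valid test, and the sample size was planned on unadjusted rates and delivers its stated power. This stands. A reader might infer that the EU primary is underpowered or wrongly tested; Step 1 shows otherwise.

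**The gain depends on an unknown correlation.** This also stands. At r = 0.2 it is about half a point, and the larger figures need r of 0.45 or more, for which the documents offer no evidence.

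**The SAP follows one consistent rule**: CMH for binary endpoints, baseline-adjusted models for continuous ones. That is fair, so the contrast with the ranked DAS28(CRP) endpoint is not a contradiction. It does show that the plan already accepts this covariate for this score.

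**Baseline activity is already examined** through the baseline table, the 5.1 subgroup and the baseline-adjusted change in DAS28(CRP), ranked first among secondaries in both sequences. This makes an imbalance visible but does not adjust the LDA comparison.

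**Not every subject need have the covariate.** It is scheduled for all, but under SAP 9.4.6, "If any observed component is missing in a window, then the observed DAS28 score will be missing". CMH by prior bDMARD keeps all Full Analysis Set subjects; an adjusted model does so only with a rule for missing baseline. This stands and shapes the fix.

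**It is too late to change the primary.** SAP 11.1 says the primary analysis and Period 1 reporting were completed under version 2.0, and Table 11 says that version incorporated FDA feedback. This is decisive against substituting the test now, though not against the point as one of design.

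**Conclusion.** The point holds as a missed efficiency gain. Continuous adjustment for baseline DAS28(CRP) would add about 0.5 to 1 point of power at r = 0.2, 1 to 1.5 at r = 0.3, 3 at r = 0.45 and 5 to 6 at r = 0.6, starting from about 90%. It costs nothing measurable at r = 0, keeps the type I error within simulation error, and guards against chance imbalance at baseline. These sizes rest on the assumed r, a normal latent score, the planning rates of 12% and 29%, and 10% non-response under NRI.

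A reader might go further and infer that the confirmatory LDA result is unsound or should be re-derived with the adjusted model. The documents do not support that: the pre-specified test is valid, and the analysis is already complete.

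**What to change.** **As a plan (design stage or later SAPs).** Analyse LDA with a logistic model containing treatment, continuous baseline DAS28(CRP) and prior bDMARD stratum. Report the standardised risk difference with a robust SE, because the model's odds ratio is conditional and the SAP reports differences in response rates. State a simple rule for missing baseline, for example mean imputation, so that all Full Analysis Set subjects are kept. Keep the current CMH as supportive. Adding the 5.1 category as a CMH stratum stays closer to the existing method but is the weaker option.

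**In this trial.** Leave the confirmatory result as it is. The adjusted LDA analysis can be added only as a supportive analysis, labelled post hoc.

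**Cost.** A paragraph of SAP text and a small programming task on data already collected. The price is a model-based estimate, and a method for LDA that differs from the one for ACR20, with which it now shares a row in Table 4.
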